The intervention will use commercially available RS-2 (Hi-Maize) that will be prepared into common bakery items, such as muffins, scones, as well as beverages such as smoothies. Control products will use the same recipe but will be prepared with regular corn starch. The RS will be Hi-Maize, a corn starch made solely from hi-amylose maize. This product is commercially available from, among others, King Arthur Flour, Honeyville and Amazon. It has been used in many published studies⁸⁵⁻⁹³ as well as at least 20 studies currently listed in ClinicalTrials.gov. Dose range has been from 15g/day to 47g/day and study duration from 1 to 8 weeks. Some people may experience flatulence and perhaps some bloating due to the higher fiber content added to their diet, therefore we will have participants do a stepwise escalation that will allow for better adaptation to the target dose of 30g. RS per day. In the first two weeks participants will consume one study food with 15 g RS per day and starting in the third week participants will consume two study foods for a total of 30g RS per day for 6 weeks. Participants will be provided with a variety of options to allow for variety. No other dietary changes will be required. Participants may consume their usual diet and participate in their usual activity throughout the study. All products will be produced at the Human Nutrition Lab in the Fred Hutch Prevention Center. See Figure 2.

Systemic inflammation will be measured as serum C-reactive protein (CRP)/albumin ratio and adiponectin. Insulin resistance will be assessed using the homeostasis model of assessment-insulin resistance (HOMA-IR). Gut microbial community structure (16S rRNA sequencing), and gut metabolites will be compared between intervention and control groups for generation of hypotheses for protective prebiotic effects on gut microbial taxa.

In order to determine whether an RS dietary intervention can potentially affect gastrointestinal tumorigenesis in high-risk individuals, participant fecal microbiota sampled will be transplanted into colorectal tumor-prone mice ([name], UW IACUC protocol # 4418_01).

[figure not shown]
Primary Aim: To determine the feasibility of an 8-week dietary intervention testing foods made with resistant starch compared to foods made with corn starch in patients who have completed treatment for stage I-III colorectal cancer. Feasibility will be assessed based on trial accrual, intervention adherence, and trial retention.

Secondary Aims:

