6. DOSAGE MODIFICATION

The dosage of the assigned study food will be modified if needed based on the participant's inability to tolerate the prescribed dosage.

Intolerance is defined as **any grade 3 or higher adverse event (AE) that is possibly, probably, or definitely attributable to the study food product.**

AEs for this study are assessed and graded in accordance with the NCI's Common Terminology Criteria for Adverse Events (CTCAE), version 5.0:

https://ctep.cancer.gov/protocoldevelopment/electronic_applications/docs/CTCAE_v5_Quick_Reference_5x7.pdf (last accessed Mar 12, 2019).

Attribution of each AE will be determined and coded by the Principal Investigator(s), in collaboration with co-investigators as needed. Attribution to study dietary intervention is categorized as follows:

1=Unrelated 2=Unlikely related 3=Possibly related 4=Probably related 5=Definitely related

AE Grade and Attribution	Dose Modification
Occurring at any time on study	
< Grade 2, any attribution	No dose reduction, proceed as planned
≥ Grade 3, unrelated or unlikely related	No dose reduction, proceed as planned
Occurring during Week 1 or 2 of study	
≥ Grade 3, possibly, probably, or definitely related	
Stop the dietary intervention and continue as follows as soon as possible (within one week) after stopping the study food product:
 
➤ Collect the Week 2 stool sample and study questionnaire. (Participant may send the Week 2 stool sample and Questionnaire by mail or deliver in person to the Prevention Center).➤ Collect the end of study fasting blood draw (originally planned for Week 8), at the Prevention Center➤ Omit all remaining activities. Provide EOS Thank You Letter and Gift Card.
Occurring during Week 3 - 8 of study	
≥ Grade 3, possibly, probably, or definitely related	Reduce the dietary intervention to 15g/day for the remainder of the study. Proceed with stool collection, fasting blood draw, and all other data collection as originally planned.

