If at any time after dose reducing to 15g/day during Week 3-8 the participant experiences new or continuing ≥ grade 3 AE(s) that are possibly, probably, or definitely related to the study dietary intervention	
Stop the dietary intervention and continue as follows as soon as possible (within one week) after stopping the study food product:
 
➤ Collect the end of study stool sample and study questionnaire (originally planned for Week 8). (Participant may send stool sample and Questionnaire by mail or deliver in person to the Prevention Center).➤ Collect the end of study fasting blood draw (originally planned for Week 8), at the Prevention Center➤ Provide EOS Thank You Letter and Gift Card.

Randomized, Controlled Trial of Resistant Starch in Stage I-III Colorectal Cancer Survivors Pilot Study: The Fiber for Health After Cancer Study

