9. DATA SAFETY MONITORING PLAN

Oversight for this study will be provided by the Principal Investigators at Fred Hutch, Drs. [name] and [name], with delegation of responsibilities to designated study personnel. Study PIs will ensure all entry criteria are met prior to the initiation of the protocol, and all study procedures and reporting of adverse events are performed according to the IRB-approved protocol.

In addition, in compliance with Fred Hutch/UW Cancer Consortium DSMP guidance, this study will be monitored by the Fred Hutch Clinical Research Support (CRS) Monitoring program. Study participants are previously treated colorectal cancer survivors in whom the study intervention is non-therapeutic. As such, the study is low risk in accordance with the Consortium DSMP guidelines. As the study is low risk, monitoring will involve a single visit by CRS Monitoring program staff or, at CRS discretion, a contracted external monitor. This monitoring visit will occur approximately 12 months after the first subject is enrolled, and will comprise, at a minimum, consent document review and eligibility review for 10% or 3 participants enrolled. Additional monitoring may occur if so recommended by the CRS Monitoring program.

This Data Safety Monitoring Plan (i.e., Section 8 of this protocol) is hereby submitted within this protocol document for IRB review and approval.

All adverse events related to the study procedures will be fully documented on the appropriate case report form(s) and entered in a study database. For each adverse event, the investigator will provide the onset, duration, intensity, treatment required, and outcome, including documentation of need for premature termination of any study procedures.

Anticipated adverse events related to this study are:

Intervention Foods Products made with resistant starch may have the same effects as a high fiber diet: mild bloating and abdominal distension might occur while on the study since the fiber content may be higher than participant's habitual diet. Most people adapt to a higher fiber intake within 3-5 days. Participants will be monitored by the study staff via telephone calls from study staff. Staff will be trained to monitor tolerance and abnormal events via short interviews and the completed daily study food and symptoms log. Study participants will be able to reach study staff by cell phone around the clock.

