Randomized, Controlled Trial of Resistant Starch in Stage I-III Colorectal Cancer Survivors Pilot Study: The Fiber for Health After Cancer Study

Preexisting Condition.

A preexisting condition is one that is present at the start of the study. A preexisting condition should be recorded as an adverse event if the frequency, intensity, or the character of the condition worsens during the study period. Participants in this study have been diagnosed and treated for rectal cancer.

Adverse event grading scale:

0= No Adverse Event (AE) or within normal limits

1= Mild Severity: Transient laboratory test alterations; discomforts noted but no disruption of daily activities; no therapy, or only symptomatic therapy required

2= Moderate Severity: Laboratory test alterations indicating injury without long-term risk; discomfort sufficient to modify normal daily activity; specific therapy required (i.e., more than symptomatic)

3= Serious Severity: Laboratory test indicating a serious health threat or permanent injury; incapacity, inability to work, inability to perform normal daily activity; hospitalization required or prolonged; emergency treatment required; life-threatening events; death.

AEs for this study are assessed and graded in accordance with the NCI's Common Terminology Criteria for Adverse Events (CTCAE), version 5.0:

https://ctep.cancer.gov/protocoldevelopment/electronic_applications/docs/CTCAE_v5_Quick_Reference_5x7.pdf (last accessed Mar 12, 2019).

Plan for unanticipated AE reporting: All unanticipated AEs related to the study procedures that are severe or serious will be reported by Drs. [name] or [name] to the IRB within 7 days of notification of the investigator.

Plan for anticipated AE reporting: All serious anticipated AEs related to the study procedures will be reported by Drs. [name] or [name] to the IRB within 7 days of notification of the investigator.

Plan for ongoing review of results: The PI will be notified within 24 hours by the research manager of any early terminations due to an adverse event.

Plan for safety review: the PI will perform a cumulative review of all adverse events and premature terminations review every 6 months after study initiation or after completion of 50% of participant visits, whichever occurs first.

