Plan for annual reporting: A summary of the investigation including all adverse events and how they were handled, enrollment, drop-outs and reason for discontinuation and any protocol modifications will be provided to the IRB on an annual basis.

Annual Reports will contain:

- a. The number of adverse events and an explanation of how each event was handled
- b. The number of complaints and how each complaint was handled
- c. The number of subject withdrawals and an explanation of why the subject withdrew or was withdrawn
- d. The number of protocol deviations and how each was handled

Any questions of food safety will be immediately reviewed with the HNL manager. The occurrence of any serious and unexpected event may prompt changes in study protocol. Any such change will be approved by the IRB before implementation.

Randomized, Controlled Trial of Resistant Starch in Stage I-III Colorectal Cancer Survivors Pilot Study: The Fiber for Health After Cancer Study

Monitoring for data integrity and safety will be the responsibility of the investigators and the CRS Monitoring program.

Investigators will include the following in routine monitoring review: A) Validity and integrity of data: Data are checked for missing, unusual, or impossible records when they are entered into the study's computer database. The investigators may consider modifications to the data collection protocol with permission from IRB if they deem the change(s) is necessary to ensure the validity and integrity of data collected. B) Enrollment rate relative to expectation: Early lags in recruitment will be rectified with increased recruitment efforts so that recruitment will be completed on time. The investigators will monitor this closely to ensure full enrollment of appropriate participants. C) Retention of participants and adherence to protocol: The investigators will monitor retention and adherence to study protocol. Adherence to the study diet will be monitored via the Daily Record that participants fill out and the uneaten foods they return.

In addition, a CRS monitoring visit will occur approximately 12 months after the first participant is enrolled, and will comprise, at a minimum, consent document review and eligibility review for 10% or 3 participants enrolled. Additional monitoring may occur if so recommended by the CRS Monitoring program.

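### In Weeks 3–8 the dose-reduction row has no upper grade limit, so the first written action after a related life-threatening event is continued feeding at 15 g/day

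*Combined protocol and SAP*

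**What the plan says.** Section 6 (Dosage Modification) defines intolerance as "any grade 3 or higher adverse event (AE) that is possibly, probably, or definitely attributable to the study food product". The definition sets a floor and no ceiling, and grading is by CTCAE v5.0.

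For related events meeting that trigger, the table gives three actions:

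- **Weeks 1–2** (dose 15 g/day): "Stop the dietary intervention and continue as follows as soon as possible (within one week) after stopping the study food product". The listed samples are then collected and the remaining activities are dropped.
- **Weeks 3–8** (dose 30 g/day), first event: "Reduce the dietary intervention to 15g/day for the remainder of the study". All data collection proceeds as planned.
- **Weeks 3–8, after that reduction:** the food is stopped if a related event of grade 3 or higher is new or continuing.

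There is no separate row for grade 4 or above, and the first Weeks 3–8 row has no temporary hold or medical clearance step.

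Section 9 (Data Safety Monitoring Plan) mentions stopping in several places. Adverse event records are to include "documentation of need for premature termination of any study procedures". It also says: "The PI will be notified within 24 hours by the research manager of any early terminations due to an adverse event". Annual reports give the number of withdrawals with an "explanation of why the subject withdrew or was withdrawn". None of these says when an affected participant must stop.

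**The concern.** Stepping down is sensible for dose-related grade 3 gastrointestinal intolerance. Section 1 says "In the first two weeks participants will consume one study food with 15 g RS per day". A related grade 3 or higher event in that period would have stopped the food, so a participant who reaches Week 3 has normally tolerated 15 g/day for two weeks. Returning to that dose is a reasoned choice.

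The reasoning does not carry over to a life-threatening event judged possibly, probably or definitely related to the food. Such a reaction need not depend on dose, and two tolerated weeks at 15 g/day do not show that further exposure is safe after it. Section 9 describes the intervention as non-therapeutic and Section 7 says there may be no direct benefit, so nothing for the participant offsets the continued exposure.

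What is at stake is the safety of an individual participant in a rare case. The feasibility endpoints and the exploratory analyses are not affected.

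**Working it through.** The plan gives no figure on this point to reproduce. The check has three parts: trace the table, look for an overriding rule, and bound the exposure.

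**1. Trace of a related life-threatening event in Weeks 3–8.**

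- It meets the grade 3 or higher trigger. The protocol cites CTCAE v5.0 without printing its grades, so taking life-threatening as grade 4 is an assumption. The result does not depend on it. The 0–3 scale printed in Section 9 puts life-threatening events in its grade 3, which the row also covers.
- First action: reduce from 30 to 15 g/day and continue.
- If the event stays at grade 3 or above, or another such related event occurs, the next row stops the food.
- If the event falls below grade 3 and does not recur, no further row applies and feeding continues to the end of the study.

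The same event in Weeks 1–2 leads to an immediate stop. That row is coherent in its own terms, because 15 g/day is the lowest dose and there is no step below it. It also shows that a stop with sample collection is already an established procedure in this table.

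**2. Search for an overriding rule.**

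| Place | What it covers | Stop rule for the affected participant? |
|---|---|---|
| Section 4.f | Early discontinuation for a pandemic or natural disaster | No |
| Section 5 | Staying at the maximum tolerated dose; refers to Section 6 | No |
| Section 9 | Documentation, notification of early terminations, IRB reports, periodic review | No |
| Section 9 | Possible protocol changes after a serious and unexpected event | No; this acts on the study |

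**3. Bound on continued exposure.** Inputs: Week 3 starts on Day 15, the final visit is on Day 56 (Section 4.e), and the reduced dose is 15 g/day (Section 6). For an event on Day d, the days left are 56 − d and the exposure is (56 − d) × 15 g.

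| Day of event | Days left | Study starch under the written row | With a stop |
|---|---|---|---|
| 15 | 56 − 15 = 41 | 41 × 15 = 615 g | 0 g |
| 35 | 56 − 35 = 21 | 21 × 15 = 315 g | 0 g |
| 56 | 56 − 56 = 0 | 0 g | 0 g |

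For comparison, exposure at this dose in Weeks 1–2 is 14 × 15 = 210 g. The bound assumes reduction from the next day, a prompt fall below grade 3, no recurrence, no interruption and full intake. The grams describe resistant starch in the active arm. The control arm receives similar foods made with regular corn starch.

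**The case against.** The case for leaving the table alone has four parts.

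**The gap is narrow.** It needs a life-threatening event, judged related to bakery-type foods, in Weeks 3–8, that falls below grade 3, never recurs, and is handled by an investigator who follows the table literally. The expected effects are gas, bloating and looser stools. Section 7 anticipates no serious events, Section 5 describes the product as well tolerated, and Section 2 excludes known wheat, gluten, dairy or egg allergy or intolerance. All of this stands and keeps the priority low.

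**Investigators can withdraw a participant anyway.** Nothing in Section 6 forbids it, and Section 9 plainly expects that some participants may be stopped early. This also stands. But the table an investigator would consult says reduce, so stopping after a first event would depart from the written instruction. Discretion does not correct the row.

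**Some material could not be seen.** The consent form, the dosing instructions and the adherence call script are listed as appendices but were not available. One of them may contain a participant-level stopping rule. The finding is therefore certain for the wording of Section 6, and limited to the available sections for the absence of a rule elsewhere. A rule in an appendix would still conflict with the row as written.

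**A cap at grade 3 does not work on the scale that Section 9 prints.** There, life-threatening events and death are themselves grade 3. This is correct, and the fix has to deal with it.

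**Conclusion.** The concern holds. In Weeks 3–8 the written first action after any related event of grade 3 or higher, however severe, is continued feeding at 15 g/day. The later stop row catches events that persist or recur. It does not catch a life-threatening event that resolves below grade 3 and stays there.

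The size is low. The extra exposure is at most 615 g of study starch per event, falling to zero by Day 56, and few or no participants are likely to be affected. The protocol gives no expected event rate, so no probability can be attached. This is a worthwhile safety correction for the sponsor to consider. It has no bearing on the trial's statistical conclusions.

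**What to change.** 1. Limit the first Weeks 3–8 reduce row to related events of CTCAE v5.0 grade 3.
2. Add a row for related events of CTCAE grade 4 or higher in any week: stop the dietary intervention and, where clinically possible, collect end-of-study samples within one week. In Weeks 1–2, collect the samples already listed in the existing stop row. Naming life-threatening events in the new row would make it independent of grade labels.
3. State that CTCAE v5.0 alone governs grading for Section 6, so that the cap works as intended.
4. If the 0–3 scale in Section 9 is then removed, keep its whole grade 3 entry as the definition of serious for the 7-day IRB reports. That entry covers laboratory evidence of a serious health threat or permanent injury, incapacity or inability to work or carry out daily activities, hospitalization needed or prolonged, emergency treatment, life-threatening events and death.

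The cost is a short table amendment with IRB review, and possibly a rare additional early stop. It needs no extra visits or participants.

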7. PARTICIPANT RISKS AND BENEFITS

Overview of Risk

While we do not anticipate any serious adverse events during this study there are some known risks associated with participation. In addition to the known risks below there may also be some unknown risks associated with participation in this study.

Risk Associated with the Intervention

Risks associated with higher levels of either resistant starch or corn starch may include: gastrointestinal discomfort, increased gas, bloating, looser stools, and increased number of bowel movements.

Blood samples. Participants may experience lightheadedness or feeling faint when having blood drawn, and/or they may experience a temporary bruise at the site of venapuncture. All efforts will be made to minimize these risks.

Stool Collections. It may be embarrassing for people to collect their own stool.

Loss of confidentiality: This is a small change that there may be loss of confidentiality. We make strong efforts to protect confidentiality by using participant ID numbers instead of names and using password-protected electronic files.

Research Related Injuries

If a participant believes they have been injured as a result of their participation in these studies, the consent form directs them to contact the Fred Hutch IRO.

If the individual should require medical care (as determined by the intervention staff), due to research-related injury, it will be provided. However, the individual or their medical insurance will be responsible for the cost of such care.

Benefits

While there may be no direct benefit of this study to participants, the study could provide important information about future recommendations of fiber levels for colorectal cancer survivors. Because risks to subjects in this study are minor, the risks are most reasonable in relation to the expected benefits.

Compensation

Participants will each be given a \$50 VISA gift card for completing the study.

Alternatives

Alternatives to participating in this research study include not participating.

8. DATA ANALYSIS PLAN

Feasibility Endpoints.

Feasibility of the study design and intervention will be assessed based on the following three criteria:

1. Accrual. The accrual rate will be estimated with a target accrual rate of full enrollment within 12 months after study activation.
2. Adherence. Adherence to the intervention will be defined as consuming 75% or more of study foods on $\geq 75\%$ of days from baseline to 8 weeks.

Randomized, Controlled Trial of Resistant Starch in Stage I-III Colorectal Cancer Survivors Pilot Study: The Fiber for Health After Cancer Study

3. **Retention.** Target retention is defined as ≥80% of enrolled participants providing blood and stool samples at 8 weeks.

Secondary Endpoints.

Secondary endpoint analyses will be considered exploratory and will be used to provide effect size estimates to be used in a future trial.

1. Assess variability in biomarkers of insulin resistance and inflammation will be assessed using descriptive statistics.
2. Assess variability in gut microbial communities from human stool samples collected during the study by changes in alpha diversity, global microbial community (beta diversity), and genera in response to the intervention. We will use multivariate and univariate approaches to assess significant changes in the microbiome in response to the intervention.
3. Fecal microbiota from “resistant starch responders” (i.e., individuals with significant resulting elevations in fecal short-chain fatty acids concentrations) will be selected as input samples in gnotobiotic mouse studies, in which mice will be fed diets with or without resistant starch in order to characterize effects on tumorigenesis in an otherwise controlled environment. We predict that the chemoprotective effect of this diet intervention will be dependent upon gut microbial metabolism.

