The participant will be sent a pre-paid, same day courier return mailing label and box to return the frozen baseline stool sample and baseline questionnaires. Depending on accessibility of the participant to his/her neighborhood courier office, the participant can either take the shipment box to the courier office, or study staff can arrange for pick-up service by the courier from the participant's home. In the event of a 'shelter in place' mandate, the latter option will be used. In the event that the courier service is not operating, the participant will be instructed to keep the study materials at home, and the stool sample in his/her home freezer, until the courier service is again operational. The first supply of study foods will be couriered to the participant for receipt on the day of the Intervention Visit 1 telephone call.

4.c. DURING INTERVENTION

Participant activities during the intervention consist of the following which are completed by the participant at home.

- Daily consumption of study foods
- Daily completion of the Daily Study Food Consumption and Symptoms Log

Phone calls (once weekly through ramp up to 30g daily then every two weeks thereafter through end of study). Study staff contact the participants via telephone to monitor adherence, collect feedback about the study (feasibility, difficulties, etc.), and give a reminder about the participant's next Prevention Center Visit. See Adherence Call Script, Appendix 15).

4.d. INTERVENTION VISIT 2 – Week 2 - Day 14

Participants return to the Prevention Center on Day 14 for the Week-2 visit. Alternatively, this visit may be conducted telephonically (using script per Appendix 18). At this visit, the participant will bring in another stool sample, the completed Study Questionnaire (Week-2 Follow Up time point), and the Daily Study Food Consumption and Symptoms Log completed for days 1-13. If the participant is unable to come to the Prevention Center, the stool sample and questionnaires can be returned by mail.

Summary of Intervention Visit 2 Activities

Participants turn in their completed Week-2 follow-up questionnaires

1. Study Questionnaire (Week-2 Follow Up)
2. Daily Study Food Consumption and Symptoms Log (for Days 1-13)

Week-2 follow-up biological samples are collected

1. Stool

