Study staff provides the participant with study supplies for the next six weeks. These supplies consist of: (1) instructions for weekly or every other week receipt of study foods from the Fred Hutch Human Nutrition Lab (foods will be mailed, couriered, or the participant may opt to pick up their foods in person); (2) the Daily Study Food Consumption and Symptoms Log with instructions to complete daily for days 14 through end of study; and (3) another stool collection kit with instructions for the 3rd intervention visit.

Study staff also reminds the participant that staff will call the participant every other week through end of study. The purpose of these calls is to check in, remind the participant to eat the study foods daily at the appropriate dosage levels, and provide the participant an opportunity to ask questions.

Randomized, Controlled Trial of Resistant Starch in Stage I-III Colorectal Cancer Survivors Pilot Study: The Fiber for Health After Cancer Study

These calls also will ascertain what specific study food products the participant would like to order from the research kitchen for his/her next batch of study foods, and how he/she would like to receive them (delivery method). (See Adherence Call Script, Appendix 15).

4.e. INTERVENTION VISIT 3 - END OF INTERVENTION – Week 8 – Day 56

Participants return to the Prevention Center on Day 56 for their Week-8 and final visit. At this visit, the participant will bring in a final stool sample, the completed Study Questionnaire (Week-8 Follow Up time point), and the Daily Study Food Consumption and Symptoms Log completed for days 14 through end of study. If participant is unable to come to the Prevention Center, the stool sample and questionnaires can be returned by mail.

Summary of Intervention Visit 3 Activities

Participants turn in their completed Week-8 follow-up questionnaires

1. Study Questionnaire (Week-8 Follow Up)
2. Daily Study Food Consumption and Symptoms Log (for Weeks 3-8)

Week-8 follow-up biological samples are collected:

3. Stool
4. Blood (fasting) -10 cc

Study staff provides the participant with End of Study Thank You Letter and \$50 Visa Gift Card.

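### Does the adherence criterion need a target share of participants and a fuller scoring rule before it can be used?

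*Combined protocol and SAP*

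**What the plan says.** The primary aim in Section 1 is feasibility: "Feasibility will be assessed based on trial accrual, intervention adherence, and trial retention". Section 8 takes the three in turn.

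- Accrual is given a "target accrual rate of full enrollment within 12 months after study activation".
- Adherence is given a definition at the level of the person: "Adherence to the intervention will be defined as consuming 75% or more of study foods on" at least 75% of days, over a window that runs from baseline to 8 weeks.
- Retention is given a proportion: "Target retention is defined as ≥80% of enrolled participants providing blood and stool samples at 8 weeks".

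Section 1 sets the schedule: one study food a day for two weeks, then "starting in the third week participants will consume two study foods for a total of 30g RS per day for 6 weeks". Section 6 allows a reduction to 15 g/day after a related event of grade 3 or higher in Weeks 3-8, and a stop in some circumstances. Section 4.f allows early termination for a pandemic or disaster.

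Intake is recorded in a daily log. Visit 2 collects the "Daily Study Food Consumption and Symptoms Log completed for days 1-13" and Visit 3 collects the "Daily Study Food Consumption and Symptoms Log completed for days 14 through end of study". Sections 4.c and 5 add staff calls about adherence, and Section 9 adds a check on uneaten foods that participants bring back.

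**The concern.** Two of the three primary criteria say what the trial as a whole must achieve, and the third does not. The share adherent can be reported, but calling the criterion met or missed would need a cut-off chosen once the share is known. That is an awkward position for one third of a primary aim.

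The per-person rule also looks open to more than one scoring. After a permitted reduction, a participant who eats everything prescribed eats half of what was first planned, and Section 8 does not say which amount is the base. A participant lost after Visit 2 leaves 13 days of returned log, and no rule covers the other 43. If the same log can make the same person adherent or not, the proportion depends on an unstated choice.

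**Working it through.** There is no stated adherence figure, sample size or power to reproduce, so the check applies the plan's own rule.

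**Inputs.** 56 days (Visit 3 is on day 56, Section 4.e); one food a day on days 1-14 and two on days 15-56 (Section 1); thresholds of 75% of foods and 75% of days (Section 8); reduction to 15 g against 30 g planned (Section 6).

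**Day window.** 0.75 × 56 = 42 qualifying days. The window is written into the rule, so days after a stop stay in the denominator with no intake. A full eater who stops after day 41 scores 41/56 = 73.2% (not adherent); after day 42, 42/56 = 75.0% (adherent). Scoring a stop after day 14 as 14/14 would need a shortened window that Section 8 does not provide. As written it is 14/56 = 25.0%.

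**Food denominator.** A reduced day gives 15/30 = 50% of the planned amount, below 75%, but 100% of the prescribed amount. For a full eater reduced from day d, qualifying days are d − 1 against plan and 56 against prescription.

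- d = 29: 28/56 = 50.0% or 56/56 = 100%.
- d = 42: 41/56 = 73.2% or 100%.
- d = 43: 42/56 = 75.0% or 100%; both adherent.

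The readings therefore disagree for full eaters reduced up to day 42, and somewhat later for someone who also missed days. The rest of the protocol leans one way. Calls after Visit 2 are meant to "remind the participant to eat the study foods daily at the appropriate dosage levels", and Section 6 speaks of tolerating a prescribed dosage. Both point to the amount currently prescribed.

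**Unlogged days.** If scored as not adherent, 14 such days in an otherwise full eater give 42/56 = 75.0% (adherent) and 15 give 41/56 = 73.2% (not). If left out, both give 100%. A participant lost after Visit 2 has at most 13/56 = 23.2% documented, so the fixed window makes that person non-adherent unless other evidence is used. The calls and returned foods are such evidence, although Section 8 does not say how to combine them with the log.

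**Effect on the proportion.** The number of participants is not in the text available, so N is assumed. At N = 30, one reclassified person moves the share by 1/30 = 3.3 points and three by 10 points. With 75% adherent, the exact 95% interval is 50.9% to 91.3% at N = 20 (15/20), 58.8% to 87.3% at N = 40 (30/40) and 62.1% to 85.3% at N = 60 (45/60).

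**What a target would add.** At an assumed N = 30, a 70% target needs 0.70 × 30 = 21 adherent and an 80% target needs 24. If the true proportion is 80%, the binomial chance of meeting them is 0.94 and 0.61. At a true 70%, the chances are 0.59 and 0.16. A trial whose true adherence sits exactly at an 80% target would miss it 1 − 0.61 = 39% of the time.

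**Two side arguments.** First, one could try to link an adherence target to retention: with 80% retained and everyone else counted as non-adherent, a 70% target needs 0.70/0.80 = 87.5% of the retained to be adherent. The link fails, because Section 4.e collects no blood at a telephone Visit 3. A participant who ate everything can then miss the retention definition and still be adherent. Second, the day count follows total intake loosely. Full intake to day 42 and none afterwards is adherent with (14 + 28 × 2)/(14 + 42 × 2) = 70/98 = 71.4% of foods. Leaving one of two foods on alternate days in Weeks 3-8 is non-adherent with (14 + 21 × 2 + 21)/98 = 77/98 = 78.6%. A day count and an amount are different summaries, and the log holds both, so this is not a fault in the rule.

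**The case for a change.** The best case for a change is that the plan set its own standard. It names three criteria and gives two of them targets, so a target for the third is not an outside demand. The intervals above are wide enough to accommodate several cut-offs picked afterwards, and a few sentences would prevent that. Dropout and pandemic termination can affect participants without any grade 3 event, so the scoring questions are not confined to rare reductions.

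Part of this stands. The missing target is an inconsistency between the three items, and the food base after a reduction is unstated. But no passage ties a go/no-go decision to adherence; feasibility is to be assessed, and an adherent proportion with its interval does that. Dropout and early termination are largely settled by the fixed window. What remains is the food base for reduced participants and the use of calls and returned foods for unlogged days. The argument also supplies no target value and no reason to prefer one, and it shows no stated number or rule in the plan to be wrong.

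**Conclusion.** No change follows. The gap is one that analysts fill sensibly: report the adherent share of enrolled participants (the base already used for retention) with an exact interval, count foods against the amount prescribed at the time, score unlogged days as not adherent unless other records show intake, and give the alternative count beside it. If no target is written beforehand, the result should be described and not labelled met or missed.

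The size of what is left open is 3.3 points per reclassified participant at an assumed N of 30, against an exact interval running from 58.8% to 87.3% at an assumed N of 40. This rests on three assumptions: that the 8-week window is read literally as 56 days, that reductions follow the related grade 3 threshold in Section 6 and are therefore few, and that the trial size is in the range assumed. The number of participants who will be reduced, stopped or leave unlogged days cannot be known from the documents.
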